## 2.2 Study Phases

**PHASE I – Adaptation of iManage****(18 months)**

During this phase we will adapt the beta version of iManage and integrate clinical guidelines for adults with SCD. During this phase, we will perform three focus groups that will include a total of fifteen adults with SCD to identify user needs and preferences for the guidelines and app. This information will be used to adapt the app which will then be tested and iteratively refined through usability sessions with 10 adults until ease of use and usefulness are high.

At the end of this phase, we will have a modified iManage that will be used in the Phase II Pilot Study.

**PHASE II Pilot Feasibility Randomized Controlled Trial****(30 months)**

Fifty participants will be enrolled or a 6-month pilot study where they will be randomized to one of two arms, standard care (control arm), or receiving iManage that will include interactive content and a fully searchable collection of the SCD-specific guidelines that are age- and health literacy-appropriate (intervention arm). An equal number of participants will be in each of the two arms (25 in each arm). They will participate in an initial visit and a 6-month follow up visit.

**PHASE III - Study Close Out and Data Analysis (12 months)**

During this phase, data analysis and manuscript preparation will occur.

**2.3 ELIGIBILITY****2.3.1 Patient Inclusion Criteria**

1. Patient must have diagnosis of SCD (Hgb SS, SC, S $\beta$ -thal)
2. Receive care at the community health clinic
3. Ability to speak and understand written English
4. Access to a smartphone
5. Age 18-70 years

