## 1.3 AIMS OF THE TRIAL

**Aim 1: Integrate clinical guidelines for adults with SCD into our beta version of iManage, an mHealth app.** Three focus groups will include a total of fifteen adults with SCD to identify user needs and preferences for the guidelines and app. This information will be used to adapt iManage which will then be tested and iteratively refined through usability sessions with 10 adults until ease of use and usefulness are high.

**Aim 2: Evaluate the feasibility and acceptability of the refined iManage in a pilot study with adults with SCD.** We will recruit 50 adults from the population of adults with SCD at the Vanderbilt Meharry Sickle Cell Disease Center of Excellence and Ohio State Sickle Cell Center for a 6-month pilot study to evaluate usability, acceptance, and usage. At the end of the study, we will conduct interviews with a subset of participants to gain an in-depth understanding of usage patterns and how

to sustain engagement to promote ongoing iManage use.

**Aim 3: Evaluate the efficacy of the refined iManage app on SCD-specific knowledge.** We will test the hypothesis that the refined iManage will increase SCD-specific knowledge by measuring SCD-specific knowledge at the start and end of the 6-month pilot study. We will conduct exploratory analyses of secondary outcomes including patient activation, adherence to guidelines, missed days of school/work, and self-efficacy.

*Specific Aim 1:*

Outcomes: The primary outcome of step 1 will be themes from focus groups that will be utilized to refine the Beta version of iManage in step 2. Outcomes from step 2 will include usability data from the System Usability Score, as well as quantitative and qualitative data about task completion.

*Specific Aim 2:*

Rationale: Technological interventions can only be successful at changing outcomes if they are feasible and acceptable. Through measurement of usability, acceptance, and usage, we can discover patterns that can lead to insights about how to modify technology to have a larger impact and reach.

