These will be the same as the usability sessions in the original protocol and consent, however, we may need to recruit additional participants for the usability sessions with the updated app for 1 to 2 rounds, requiring an additional 10 participants who may need to be recruited, increasing total recruitment for this study to 85. All the usability questions, recruitment, and consent will be the same as the prior questions.

*Specific Aim 2 & 3:*

Participants will participate in two visits, an initial visit where participants will complete the surveys shown in Table 1, where the participant will be randomized into control arm or intervention arm (1:1 ratio), and if in the intervention arm, the research team will introduce and demonstrate the iManage app. At a 6-month follow up visit, surveys will be repeated, and the research team will conduct a semi-structured interview about what they liked about the mHealth app, what they didn't like, what barriers they had to using the app, how the mHealth app could be improved, and an example of when the app helped them with care of their SCD. Interviews will take place either in person or remotely via phone or web meeting service (such as GoToMeeting). When conducting remote interviews, we will record audio using software such as GoTo Meeting or Skype. All recording files will be saved to an encrypted drive, which can only be accessed by study team members. Once a file has been removed from the secured recording media and stored on the encrypted drive, it will be deleted from the recording media.

KSP trained in human subjects research will obtain consent and administer the surveys and interview. A member of the KSP will set up and instruct the participant on how to access the mHealth app on their mobile phone, how to login to the intervention using his/her unique study identifier. The KSP will provide a 10-minute demonstration of the mHealth app, and have the participant interact with the app as independently as possible for 10 minutes to complete assisted tasks to gain knowledge and confidence to take action independently. KSP will be available to assist with questions. Participants may also get emails periodically throughout the study to ask them if they have questions about the study or the guidelines.

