**3.0 EVALUATIONS****3.1 Patient Evaluations**

Participants will provide written informed consent on paper or through REDCap e-consent and sign an authorization to use or disclose personal health information (PHI) form. Participants will get a \$250 check or gift card if they are in the 4-hour focus groups and a \$100 check or gift card if they are in the 90-minute usability session. For the pilot study, they will be compensated with a \$25 gift card for their initial visit and \$50 for their 6-month follow up visit. Both visits should take about 60 minutes. All checks or gift cards will be mailed or sent electronically. During the initial visit, participants will complete surveys, and if randomized to the intervention arm, the research team will introduce and demonstrate the iManage app. At a 6-month follow up visit, surveys will be repeated, and the research team will conduct a semi-structured interview about what they liked about the mHealth app, what they didn't like, what barriers they had to using the app, how the mHealth app could be improved, and an example of when the app helped them with care of their SCD. KSP trained in human subjects research will obtain consent and administer the surveys and interview. All survey instruments will be available in electronic form (through Research Electronic Data Capture, or

REDCap) and administered via iPads. Paper forms will also be available, and KSP will be available to answer questions. The interview will be audio recorded, transcribed, and de-identified for analysis.

Table 1 Time when each activity will be completed, and time to complete each activity			
Activity or Measure	Initial visit	6-month follow up	Time (mins)
Enrollment/Consent	X		20
Demographics	X		5
Demonstration of iManage	X		20
SCD-specific knowledge	X	X	5
SCD Specific Self Efficacy Assessment 	X	X	5
Patient Reported Outcomes Measurement Information System (PROMIS) measures	X	X	10
Patient Activation Measure 	X	X	5
Adherence to guideline measurements	X	X	5
Patient-centered Outcomes Questionnaire 	X	X	5
PHQ-9	X	X	1
REALM-SF	X	X	3
Medication adherence (Visual Analogue Scale (VAS) (1 item) and modified Morisky Scale (8 items))	X	X	1
Barriers to care	X		3
iManage usage and usability Satisfaction/acceptability questionnaire (11 items)		X	10
Semi-structured interview		X	30
Compensation	\$25	\$50	

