## **5.0 DATA MONITORING**

The local principal investigator and/or members of the research team will monitor the study for inclusion/ exclusion criteria, accrual/withdrawal rates, and breech of confidentiality annually prior to submission to the IRB. Any adverse events will be reviewed immediately with the Principal Investigator and will be reported to the Ohio State IRB per IRB regulations. All study events will be summarized once a year for the IRB, during the annual continuing review reporting.

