## **6.0 REGISTRATION AND STUDY ORGANIZATION**

Approval for use of this protocol and consent forms by the Institutional Review Board (IRB) must be obtained prior to patient participation on the trial. All reasonable measures will be taken to protect the confidentiality and identity of the patient and patient's records according to State and Federal laws. Patient identity will not be revealed in any publication.

The parent/legal guardian of each patient will be given consent forms to read and sign on paper or through REDCap e-consent prior to the patient's entry into the trial, if eligible. These forms will contain a description of the objectives of the trial, a description of the examinations and tests which will be given to the patient as each part of the trial, as well as expectations of the patient as a trial participant. These consent forms will be given to the patient by a KSP.

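### Do the unnamed clinic in inclusion criterion 2 and the guardian signature in Section 6.0 call for a change to the plan?

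*Combined protocol and SAP*

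**What the plan says.** **Where participants come from.** Criterion 2 in Section 2.3.1 reads "Receive care at the community health clinic". It refers to a single clinic, gives no name, and the term is not used again. Aim 2 in Section 1.3 draws the 50 pilot participants "from the population of adults with SCD at the Vanderbilt Meharry Sickle Cell Disease Center of Excellence and Ohio State Sickle Cell Center". Section 5.0 says that the local principal investigator or the research team "will monitor the study for inclusion/ exclusion criteria, accrual/withdrawal rates" once a year.

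**Who signs.** Section 6.0 states: "The parent/legal guardian of each patient will be given consent forms to read and sign on paper". The same paragraph ends: "These consent forms will be given to the patient by a KSP". Section 2.3.1 sets "Age 18-70 years", and Section 3.1 states: "Participants will provide written informed consent on paper or through REDCap e-consent".

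**The concern.** Read literally, criterion 2 would exclude a patient of either named centre who is not seen at the clinic, although Aim 2 counts that patient in the recruitment population. It is also the only site-of-care rule among the eligibility criteria, and it is one of the rules that the annual monitoring is meant to check. Two staff members could then classify the same patient differently, and the report could be vague about whom the result describes.

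The consent wording looks worse on its face. A guardian's signature does not fit a trial of adults, and the protocol appears to give two answers on who authorises participation. Because the sentence covers each patient, it cannot be read as a provision for the occasional adult who lacks capacity.

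**Working it through.** The point is mainly textual, so the check sets the sections side by side and then asks whether any planned figure depends on them.

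**1. Clinic against centres.** Section 1.3 names two centres; Section 2.3.1 names one clinic and does not identify it. Nothing in the text reviewed says whether the clinic is part of a centre, affiliated with one, or separate. The page before the table of contents was not in that text, so a definition there cannot be ruled out. The documents therefore show an undefined term. They do not show a contradiction, because a clinic inside or linked to a centre would be consistent with both sections.

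**2. Guardian against participant.** Four statements bear on who signs:
- Section 2.3.1: ages 18 to 70 only.
- Section 3.1: the participant consents, and trained study staff obtain the consent. Section 2.1 also has study staff obtain it.
- Section 6.0, last sentence: the forms go to the patient.
- Section 6.0, guardian sentence: the parent or guardian signs.

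The first three agree and the fourth stands alone.

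**3. How many people the guardian sentence literally covers.** Section 1.3 gives 15 focus-group, 10 usability and 50 pilot participants, all described as adults. Section 2.1 adds 10 usability participants under the same recruitment and consent, "increasing total recruitment for this study to 85". The sum agrees: 15 + 10 + 50 + 10 = 85. The sentence fits none of them. That is the reach of a drafting slip and does not measure an effect.

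**4. Does the power figure depend on either point?** Section 4.2 uses N = 50, a mean paired difference of 1.1, a standard deviation of differences of 2.5, and two-sided alpha of 0.05. The difference comes from a 15% gain on a baseline of 7.5: 0.15 × 7.5 = 1.125, taken as 1.1.
- Noncentrality: (1.1 / 2.5) × √50 = 0.44 × 7.071 = 3.11, with 49 degrees of freedom.
- Exact paired t-test power: 86.21%, against 86.2% stated.

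The score inputs come from earlier studies cited in Section 4.2, and N is a fixed target. None changes with the clinic's identity or with who signs. Whether a paired test suits a two-arm trial is a separate question.

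**5. Could either point bias the comparison?** Section 6.0 puts consent before entry and makes entry conditional on eligibility, and Section 2.1 randomises at the initial visit. A wider or narrower reading of criterion 2 therefore acts before allocation. It alters who enters the trial but does not favour an arm.

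**The case for a change.** The strongest case for acting is that the protocol is the standard for any eligibility check, that what staff know informally is not written down, and that who may enrol and who consents are core statements which two one-line edits would settle. The mismatches do stand, and tidying them whenever the protocol is next amended would do no harm.

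The rest of the case is weaker. Criteria 1, 3, 4 and 5 can be checked as written, so only one of five is unclear, and nothing in the documents shows that patients were, or would be, classified differently. The obvious edit, opening criterion 2 to patients of both centres, presumes a relation that the documents do not give and could widen a restriction the investigators intended. Criterion 2 is also not limited to the pilot, whereas Section 1.3 names the centres only for Aim 2. On consent, Section 6.0 itself requires ethics board approval of the forms before anyone takes part. Those forms, which were not in the text reviewed, are what a participant actually signs.

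A related suggestion is to state an allocation method stratified by centre, since Sections 2.1 and 2.2 promise 1:1 and 25 per arm without giving one. This concerns neither eligibility nor consent. Permuted blocks of 4 in two centres totalling 50 leave centre remainders of (0, 2), (2, 0), (1, 1) or (3, 3). Each allows a total arm difference of up to 2, that is 26/24, so the method would not guarantee 25/25. The imbalance itself hardly matters: the standard error relative to equal arms is √[(1/26 + 1/24) / (2/25)] = 1.001. Adjusting for centre would also depend on a between-arm model that Section 4.1 does not specify.

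**Conclusion.** No change to the plan follows. The clinic is a missing detail that site staff can fill in when they screen and that the report can state when it describes where participants were recruited. The guardian sentence is a clerical slip, overridden by the consent procedure in Section 3.1 and by the close of its own paragraph. Neither affects the sample size (50 in the pilot, 85 overall), the stated power (86.2%), the analysis or the conclusions, and no safety consequence is shown. The effect of criterion 2 on accrual is unknown and cannot be bounded from the documents.

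This rests on two assumptions: that screening staff at the participating centres know which clinic is meant, and that the approved consent forms name the adult participant as signatory, as Section 3.1 describes. If the clinic proved to be unrelated to either centre, criterion 2 and Aim 2 would truly conflict and would have to be reconciled, but nothing in the documents indicates that.

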**2.3.2 Patient Exclusion Criteria**

1. Lack of access to smartphone
2. Inability to understand written English

**3.0 EVALUATIONS****3.1 Patient Evaluations**

Participants will provide written informed consent on paper or through REDCap e-consent and sign an authorization to use or disclose personal health information (PHI) form. Participants will get a \$250 check or gift card if they are in the 4-hour focus groups and a \$100 check or gift card if they are in the 90-minute usability session. For the pilot study, they will be compensated with a \$25 gift card for their initial visit and \$50 for their 6-month follow up visit. Both visits should take about 60 minutes. All checks or gift cards will be mailed or sent electronically. During the initial visit, participants will complete surveys, and if randomized to the intervention arm, the research team will introduce and demonstrate the iManage app. At a 6-month follow up visit, surveys will be repeated, and the research team will conduct a semi-structured interview about what they liked about the mHealth app, what they didn't like, what barriers they had to using the app, how the mHealth app could be improved, and an example of when the app helped them with care of their SCD. KSP trained in human subjects research will obtain consent and administer the surveys and interview. All survey instruments will be available in electronic form (through Research Electronic Data Capture, or

REDCap) and administered via iPads. Paper forms will also be available, and KSP will be available to answer questions. The interview will be audio recorded, transcribed, and de-identified for analysis.

Table 1 Time when each activity will be completed, and time to complete each activity			
Activity or Measure	Initial visit	6-month follow up	Time (mins)
Enrollment/Consent	X		20
Demographics	X		5
Demonstration of iManage	X		20
SCD-specific knowledge	X	X	5
SCD Specific Self Efficacy Assessment 	X	X	5
Patient Reported Outcomes Measurement Information System (PROMIS) measures	X	X	10
Patient Activation Measure 	X	X	5
Adherence to guideline measurements	X	X	5
Patient-centered Outcomes Questionnaire 	X	X	5
PHQ-9	X	X	1
REALM-SF	X	X	3
Medication adherence (Visual Analogue Scale (VAS) (1 item) and modified Morisky Scale (8 items))	X	X	1
Barriers to care	X		3
iManage usage and usability Satisfaction/acceptability questionnaire (11 items)		X	10
Semi-structured interview		X	30
Compensation	\$25	\$50	

### 3.2 Outcomes:

To test our hypothesis, we will measure the change in the primary outcome of SCD-specific knowledge between the initial visit and the 6-month follow up visit (Table 1). We will measure the change in the following secondary outcomes: (1) patient activation; (2) patient and provider adherence to SCD-specific guidelines; and (3) self-efficacy. Other secondary outcomes we will assess during the pilot study period are measures from a patient-centered questionnaire, including missed days from school or work and days home in pain, barriers to care, medication adherence, PROMIS measures (Computer Adaptive Tests), PHQ-9, health literacy (through REALMSF), and acute health care utilization, specifically total emergency department (ED) visits and hospitalizations. We've elected to use all cause ED visits and hospitalizations as opposed to SCD-specific health care utilization because adults with SCD believe all-cause ED visits and hospitalization is a stronger measure of their well-being than SCD related health care utilization. We will collect ED and hospitalization data by having all participants sign information release forms during consent to track acute health care utilizations at area facilities for at least six months. Adherence to SCD guidelines: Guideline adherence is a bi-directional patient-provider interaction. We will assess whether there is documentation of recommending guidelines in the electronic medical records and see how this compares to what patients report in iManage. Missed days from school or work: Patients will report on days missed from school or work because of illness at the 6-month follow up visit. We will also inquire about other opportunities a patient has missed because of SCD (for example missed opportunities for school or work, including having to drop out of school or work or being fired from their job). Other outcomes include SCD-specific measures of self-efficacy and patient activation, using the validated Sickle Cell Self-Efficacy Scale and the Patient Activation Measure. These instruments were validated in prior studies demonstrating rigor and reproducibility.

We will measure usability and acceptability of iManage through surveys at the 6 month follow up, and we will measure usage of iManage throughout the 6-month period. Usability will be measured by the widely used and validated System Usability Scale. We will measure acceptability with a validated survey instrument based on the technology acceptance model introduced by Gao et al. The mobile health application for the guidelines has built-in tracking of the number of times the application is launched, how many times each of the functions are used, and how many times each button has been pushed. To measure usage, we will record the numbers of each of these events for each adult. In addition to total use, we will measure usage over time including any use, initial use, periodic use, and sustained use.

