Outcomes: We will measure usability and acceptability of iManage through surveys at the 6 month follow up, and we will measure usage of iManage throughout the 6-month period. Usability will be measured by the widely used and validated System Usability Scale. We will measure acceptability with a validated survey instrument based on the technology acceptance model introduced by Gao et al. The mobile health application for the guidelines has built-in tracking of the number of times the application is launched, how many times each of the functions are used, and how many times each button has been pushed. To measure usage, we will record the numbers of each of these events for each adult. In addition to total use, we will measure usage over time including any use, initial use, periodic use, and sustained use. We will also use a satisfaction/acceptability questionnaire to help evaluate acceptability of the app.

*Specific Aim 3:*

Rationale: Currently, health care providers provide education about SCD at clinic visits yet, data show that technology solutions designed to improve SCD knowledge are effective. We hypothesize that delivering NHLBI SCD-guidelines via an mHealth app, iManage, will increase patients' SCD-specific knowledge

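### As written, app usage includes the supervised session at the initial visit, so any use is close to 25/25 and cannot show voluntary uptake

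*Combined protocol and SAP*

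**What the plan says.** All references are to the combined protocol and SAP.

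- **Source of the data.** Section 3.2 (and Section 1.3, Specific Aim 2) relies on "built-in tracking of the number of times the application is launched, how many times each of the functions are used", together with button pushes.
- **What is counted.** "To measure usage, we will record the numbers of each of these events for each adult". No type or date of event is left out.
- **Period.** "we will measure usage of iManage throughout the 6-month period". The text does not say whether this begins at the visit or after it.
- **Summaries.** "In addition to total use, we will measure usage over time including any use, initial use, periodic use, and sustained use". None of these terms is given a window or threshold.
- **The supervised session.** Section 3.1 places it at the initial visit: "if randomized to the intervention arm, the research team will introduce and demonstrate the iManage app". Section 2.1 (Specific Aim 2 & 3) gives the detail. Staff set up access on the participant's phone and explain "how to login to the intervention using his/her unique study identifier". Then "The KSP will provide a 10-minute demonstration of the mHealth app", after which staff "have the participant interact with the app as independently as possible for 10 minutes to complete assisted tasks". Table 1 allots 20 minutes to the demonstration at the initial visit and none at six months.
- **Analysis.** Section 4.1 gives general descriptive and association methods. Section 4.3 puts app data into the analysis file. Neither mentions a filter for visit-day events or a separate training account.

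**The concern.** Aim 2 asks whether adults with SCD will use the app, and the rationale in Section 1.3 makes its success depend on that. Any use is the simplest measure of uptake, and it is useful only if a participant who ignores the app can score zero.

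Under the stated counting rule, almost nobody can. The assisted tasks are done in the participant's own app, and the instruction given is to log in under the participant's own identifier. A person who never reopens the app after the visit therefore still has at least one launch and some function use on record. The pilot could report near-complete use as a feasibility result when it only confirms that the training took place. The same events enter total use, and they enter initial use unless that term is later defined to exclude them.

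**Working it through.** **1. The plan's own figure.** No target or precision is stated for usage. The only power figure, in Section 4.2, concerns knowledge: n = 50, mean paired difference 1.1, SD of differences 2.5, two-sided alpha 0.05, paired t-test.

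- Noncentrality = (1.1 / 2.5) × √50 = 0.44 × 7.071 = 3.11, on 49 degrees of freedom.
- Noncentral-t power = 86.21%, against the stated 86.2%. It reproduces.
- Usage does not enter this calculation, so nothing below changes it.

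**2. Inputs for usage.**

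- Planned intervention arm: 25 (Section 2.2, 50 randomised 1:1).
- Supervised session: 10 minutes of demonstration plus 10 minutes of assisted tasks (Section 2.1), which agrees with the 20 minutes in Table 1.
- Number who open the app after the session, x: not given anywhere, so it is varied below.

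**3. Any use under each rule.**

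- Session counted: each participant who completes it has at least one logged event, so any use = 25/25 = 100% for every x from 0 to 25.
- Session excluded: any use = x/25.
- Overstatement = (25 − x)/25.

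| Assumed x | Session counted | Session excluded (exact 95% CI) | Overstatement |
|---|---|---|---|
| 10 | 100% | 40% (21% to 61%) | 60 points |
| 15 | 100% | 60% (39% to 79%) | 40 points |
| 20 | 100% | 80% (59% to 93%) | 20 points |
| 23 | 100% | 92% (74% to 99%) | 8 points |

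The exact lower limit for 25/25 is 0.025^(1/25) = 0.863. That interval has no useful meaning here, because the counting rule fixes the proportion.

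**4. The other usage measures.**

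- *Total use* gains the events of one session per person. The documents do not say how many that is, so the inflation cannot be sized.
- *Initial use* starts with the supervised session. Whether it contains anything else depends on a definition the plan does not give.
- *Periodic and sustained use* describe use spread over time. One session on the first day can hardly produce either.

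**5. Associations.** Section 4.1 names Pearson or Spearman correlation for two continuous measures. If the session adds about the same count c to everyone, then corr(X + c, Y) = corr(X, Y), and the ranks do not change. Only differences between people in session activity add noise. A yes/no any-use variable equal to yes for everyone has no variation and cannot be cross-tabulated usefully.

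**The case against.** The strongest reply is that this rests on silence. The usage terms are undefined, the start of the six months is not fixed, and a team that began counting after the visit would not contradict the protocol. That is true, and it limits the claim to what follows from the text as written. It does not remove the point. The text does state which events are recorded, for whom and over what period, and following it gives an uninformative result. Leaving the choice open means making it after the log has been seen.

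A reader might also draw stronger conclusions, which the documents do not support:

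- *That the trial cannot report uptake.* It can. Measuring usage over time implies that the log holds timing, so uptake can be recovered. Periodic and sustained use and the six-month interview on barriers would also reveal someone who stopped on the first day.
- *That initial use is simply the staff demonstration.* Section 2.1 separates the demonstration from the participant's own assisted tasks and does not say whose login the demonstration uses. Initial use could also mean the first weeks. It is contaminated by the session, but is not shown to consist of it.
- *That any link between use and knowledge is spoiled.* A roughly constant addition barely moves a correlation, and no analysis of use against knowledge is specified.

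It is also fair to say that usage is descriptive here: no progression rule, test or sample size depends on it.

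**Conclusion.** The point holds in a limited form. On the counting rule as written, any use is about 25/25 whatever happens after the visit, so it cannot show voluntary uptake. Total and initial use are inflated by an amount the documents do not allow to be calculated. Periodic and sustained use are largely unaffected, and the primary knowledge outcome and its 86.2% power are wholly unaffected.

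This rests on two assumptions. The first is that participants complete the session as Section 2.1 describes; a failed set-up or a skipped session would bring the figure below 25/25. The second is that events in the session are logged under the participant's identifier, which is the plain reading of the login instruction. The 40-point overstatement at 15 of 25 is an illustration, not an estimate. This should be corrected because it affects a named Aim 2 outcome and is easy to repair, but it does not threaten the trial's main comparison.

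**What to change.** In Sections 1.3 and 3.2, state that total, any, initial, periodic and sustained use are computed only from events logged after the supervised session ends. Cutting at the end of the session, not at the following day, keeps genuine use later on the same day. There is no matching case for dropping the day of the six-month visit, since Table 1 schedules no app demonstration then.

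Report the session's events separately as training exposure. Use everyone randomised to iManage as the denominator, so that a participant with no post-session events counts as a non-user whether or not set-up succeeded. The same edit is a good place to give initial, periodic and sustained use a window and a threshold.

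The cost is a sentence or two of text and a filter on a log that is already being kept. Session events must be flagged by timestamp, so staff need to note when each session ends. Reported usage will look less favourable. The sample size and the power do not change.
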